9.2 SETTING

The study will be conducted in a general practice setting, Korea National Health Insurance claim data & mortality data from the Bureau of Statistics, which includes computerized medical records of more than half million patients in South Korea. The maximal observation period will be from Jan 2005 to Apr 2016.

- Inclusion criteria
 - Diagnosed with COPD [**based on ICD-10 code(J43.x-44.x except J430), as the primary or within the fourth secondary diagnosis and initiated LAMA or ICS/LABA more than twice a year from Jan 1, 2005 to Apr 30 2016**].
 - Age >55 years old as of 2005 when enroll started
- Exclusion criteria
 - Prescription history with any long acting bronchodilator for maintenance therapy (the patient should be inhaler naïve) from 2002 to 2005.
 - Prescription history with ipratropium bromide
 - Prescription history with Leukotriene receptor antagonist(LTRA) or ICS
 - Prescription history of LABA/LAMA FDC
 - Patients with lung cancer, IPF, ILD or lung transplantation at the time of COPD diagnosis

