9.3.1 Exposures

The exposure measures are based on the prescription of LAMA or fixed dose combination of ICS/LABA. Using the medication possession ratio (MPR), to describe adherence, the case of overall

mean MPR $\geq 80\%$ defined as good adherence. Therefore, usually one inhaler is used per month, this study includes patients who have been prescribed total more than 10 inhalers per 12 months (1 year).

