9.3.2.2 Secondary outcomes

Secondary endpoint

- Health care utilization : Medical cost / number of annual visits, prescriptions and hospitalizations (hospitalization mainly due to severe exacerbation of COPD) over one year.
- All-cause mortality
- Recorded incidence of lung cancer (based on ICD-10 code C34.XX)

[REDACTED]

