9.7 DATA ANALYSIS

The study population consists of COPD patients that have received LAMA and ICS/LABA treatment. The study consists of three stages: a) identification and extraction of LAMA-exposed and ICS/LABA-

exposed cohort, b) matching between LAMA-exposed and ICS/LABA-exposed and c) descriptive analysis of cohorts and analysis of outcomes.

Detailed methodology for summary and statistical analyses of data generated in this study will be documented in an SAP. The SAP may modify the plans outlined in the protocol; any major modifications of primary endpoint definitions or their analyses would be reflected in a protocol amendment.

For the purpose of this study, analyses will be conducted using SAS statistical software and R. To address the imbalance of potential confounders between LAMA ICS/LABA groups, we matched treatment groups using propensity scores estimated as by multiple logistic regression analysis *based on* as age, sex, socioeconomics status, *Charlson Comorbidity Index*, and asthma, history of COPD exacerbation. Demographics and clinical characteristics will be tabulated. Frequencies and percentages will be presented for categorical variables. For continuous variables, means, standard deviations, and ranges, or medians and inter-quartile ranges, will be reported as appropriate. We used a standardised difference to compare baseline characteristics between COPD patients who were treated with LAMA and those treated with ICS/LABA. The matched Cox proportional hazards regression analyses will be used to estimate hazard ratios (HRs) HRs and 95% confidence intervals (95% CIs) for all outcomes. For (possibly) repeating events (such as *exacerbation event*) *additionally* a Poisson regression model will be fitted for the number of events (taking into account the matching). The cox and Poisson models will be adjusted for unbalanced PS-variables at baseline. Mortality was estimated by the Kaplan-Meier method, and results were compared between groups using the log-rank test.

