9.7.1.1 Propensity score methodology

The propensity score will model the likelihood among COPD patients of receiving LAMA and ICS/LABA. The model for the propensity score will to the extent possible include the following elements:

- 1) Age and sex
- 2) Socioeconomic status (e.g. income, educational level, single living)
- 3) History of COPD exacerbation
- 4) Charlson Comorbidity Index
- 5) History of asthma

A logistic regression analysis will be performed on the identified COPD patients where treatment with LAMA and ICS/LABA groups is the dependent, dichotomous variable and the independent variables are listed above (age, sex and history of COPD exacerbation et al.). Based on this analysis, the propensity score is calculated for each patient. For subgroup analyses, PS matching and evaluation of its success, as presented below, will be re-done as covariate balance is not automatically maintained in sub-cohorts.

Smoking may be an important confounder in COPD but smoking status is usually not available in the databases at all. If smoking status is confirmed to be available, the data will be analysed with and without smoking status included in the model and the magnitude of the confounding effect assessed (sensitivity analysis).

PS matching will be done in a 1:1 ratio using the nearest-neighbor algorithm, using calipers of width equal to 0.2 of the standard deviation of the logit of the PS (matches of the main exposure sub-cohort and the comparator sub-cohort are formed if the caliper width is not exceeded for the logit of PS). For LAMA-exposed patient to ICS/LABA-exposed patients will be selected within the same matching interval of the propensity score. The distribution of propensity scores will be examined between LAMA-exposed and eligible ICS/LABA-exposed. In the matching procedure, matched comparator sub-cohort patients (ICS/LABA) will be removed from the pool of eligible patients among the comparator sub-cohort so that a matched patient is no longer available for consideration as a potential match for another exposed patient.

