9.7.2 Main analysis

For the primary effectiveness outcomes incidence rates (events per 1,000patients-years) with corresponding 95% confidence intervals (CI) will be calculated. This will be evaluated by a matched Cox proportional hazards regression model for counting processes, which allow the follow-up time to be divided into several periods and therefore control for baseline and time-dependent covariates, using the full observational period of available data, i.e. up to 11 years of follow up. The Cox proportional hazards regression will take into account the fact that individual matching (1:1) will be performed by considering the exposed patient and his/her matched controls as one stratum and including this as a stratum in the Cox proportional hazards model. Additional variables will be included in the model if available. The cumulative incidence plots will be accompanied by number of patients at risk at different time points during follow-up. For (possibly) repeating events (such as exacerbation event) additionally a Poisson regression model will be fitted for the number of events (taking into account the matching). Time in the study will be included as an offset variable in the model. The cox and Poisson models will be adjusted for unbalanced PS-variables at baseline.

The outcome will be analyzed separately for each:

- 1) Primary outcome
 - Comparison of pneumonia incidence in COPD patients using LAMA and ICS/LABA
 - Comparison of exacerbations frequency and rate in COPD patients using LAMA and ICS/LABA : moderate or severe exacerbation

Proprietary confidential information © 2022 Boehringer Ingelheim International GmbH or one or more of its affiliated companies

[figure not shown]
- Comparison of time to start triple combination therapy (time from initial 'LAMA mono' or ICS+LABA' to 'LAMA+LABA+ICS' combination) in COPD patients using LAMA and ICS/LABA

2) Secondary outcome

- Comparison of all-cause mortality differences in COPD patients using LAMA and ICS/LABA
- Comparison of lung cancer incidence in COPD patients using LAMA and ICS/LABA
- Comparison of health care utilization: Medical cost / No. of prescriptions, visits and hospitalizations (hospitalization mainly due to severe exacerbation of COPD)

Health care utilization

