9.12 BIAS

This study will include users of LAMA and ICS/LABA. Immortal time bias will be minimal, as the follow-up will begin at the initiation of drug use. Adherence to drug use will be unknown.

Comparing the outcomes between users of LAMA and ICS/LABA will decrease confounding by indication, as the comparison group will have a similar indication to drug use than the patients in the LAMA-exposed cohorts.

The compared sub-cohorts will be matched on the basis of PS. The PS will be computed on the basis of a wide range of covariates related to sociodemographic characteristics, history of exacerbation, other comorbidities, and prior/concomitant use of other drugs. The PS matching will decrease the systematic differences between the sub-cohorts and, thus, decrease confounding.

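### Lung cancer is counted from inhaler start with no visible lag, and known cancer is excluded only at COPD diagnosis, so cancers already present at the index date can count as incident

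*Combined protocol and SAP*

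**What the plan says.** Section 9.3.2.2 defines the outcome in one line: "Recorded incidence of lung cancer (based on ICD-10 code C34.XX"). It gives no lag, latency window or rule for early codes.

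Section 9.12 sets time zero: "the follow-up will begin at the initiation of drug use". Section 9.7.2 lists "Comparison of lung cancer incidence in COPD patients using LAMA and ICS/LABA" among the secondary comparisons and describes the Cox analysis as "using the full observational period of available data, i.e. up to 11 years of follow up". Section 9.7 says that matched Cox models "will be used to estimate hazard ratios (HRs) HRs and 95% confidence intervals (95% CIs) for all outcomes", which includes lung cancer. Section 9.7.2 makes each 1:1 matched pair a stratum.

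One safeguard is visible. Section 9.2 and the abstract exclude "Patients with lung cancer, IPF, ILD or lung transplantation at the time of COPD diagnosis". The reference date is the COPD diagnosis, not the first inhaler.

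Section 9.3.1 adds an adherence rule: "this study includes patients who have been prescribed total more than 10 inhalers per 12 months (1 year"). It decides who enters. It is not stated to move time zero.

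**The concern.** A cancer that is present when the inhaler is started cannot be a result of that inhaler. Lung cancer and COPD share symptoms such as cough and dyspnoea, so an undiagnosed cancer can prompt the first prescription, and the work-up around initiation can bring the diagnosis forward.

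Two groups get past the exclusion in 9.2:

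- patients whose C34 code is first recorded after COPD diagnosis but before the index date;
- patients whose cancer is present but not yet recorded at the index date.

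The first group need not be empty. Section 9.7.1 matches on years since COPD diagnosis, so the plan itself allows a gap between diagnosis and treatment.

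At stake is whether the lung cancer hazard ratio compares cancers arising after treatment or a mixture of those and pre-existing ones. Equal amounts of pre-existing cancer dilute a real difference. Unequal amounts bias the ratio. Equality cannot be assumed: section 9.7.1.1 says smoking status is usually unavailable, and smoking is not among the listed propensity score variables.

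**Working it through.** The documents give no lung cancer rate, effect size or power, so there is no planned figure to reproduce. From the documents come the window January 2005 to April 2016 (11.33 years), 1:1 matching, and at least 5,000 patients per arm. Every other input is an assumption. Hazard ratios (HR) are ICS/LABA over LAMA.

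**1. Share of follow-up in year 1.** Assume uniform entry over A = 11.33 years and mortality m of 3% to 9% per year. The proportion still followed at time t is (1 − t/A)·exp(−mt). Integrating from 0 to 1 and dividing by the integral from 0 to A:

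- m = 0.03: 0.942 / 5.076 = 18.6%
- m = 0.09: 0.915 / 4.146 = 22.1%

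With each pair as a stratum, an event informs the HR only while both members are at risk. With independent entry dates within pairs, the integrand is squared:

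- m = 0.03: 0.888 / 3.214 = 28%
- m = 0.09: 0.839 / 2.432 = 35%

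**2. Dilution if year-1 events carry no effect.** Let w be the share of events in year 1. On the log scale the observed HR is about exp[(1 − w)·ln HR]. For a true HR of 1.30:

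- w = 0.2: exp(0.8 × 0.2624) = 1.23
- w = 0.4: exp(0.6 × 0.2624) = 1.17

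A true HR of 1.0 stays 1.0. The value w = 0.2 is close to the person-time share in step 1, so it contains hardly any excess of pre-existing cancer. The shift to 1.23 comes from treating all year-1 events as unrelated to the drug.

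**3. Pre-existing cancer modelled directly.** Assume N = 5,000 per arm, incidence λ = 5 per 1,000 person-years (range 3 to 8), follow-up T = 5 years (range 3 to 8), and undiagnosed cancer at start in a proportion p of 0.5% to 1%. All pre-existing cancers surface in year 1, on average at mid-year. Deaths are ignored.

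- Events = N[p + (1 − p)(1 − exp(−λT))]
- Person-years = N[0.5p + (1 − p)(1 − exp(−λT))/λ]

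At central values, p = 0.5% gives 147.8 events in 24,579 person-years per arm, and p = 1% gives 172.2 in 24,468. With a true HR of 1.0, the pre-existing share is 50/295.7 = 17% or 100/344.4 = 29% of all events (7% to 53% over the ranges).

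| True HR | p, LAMA | p, ICS/LABA | Observed HR, central | Over the ranges |
|---|---|---|---|---|
| 1.0 | equal | equal | 1.00 | 1.00 |
| 1.4 | 0.5% or 1% | same | 1.33 or 1.29 | 1.37 to 1.19 |
| 0.7 | 0.5% or 1% | same | 0.75 or 0.79 | 0.72 to 0.86 |
| 1.0 | 0.5% | 1% | 1.17 | 1.08 to 1.36 |
| 1.0 | 1% | 0.5% | 0.85 | 0.73 to 0.93 |

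For example, the fourth row is (172.2/24,468) / (147.8/24,579) = 1.17. In this model a one-year lag restores the true HR by construction.

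**4. Price of a lag.** If a share w of events is dropped, the confidence interval on the log scale widens by 1/√(1 − w): 1.12 for w = 0.2 and 1.29 for w = 0.4.

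**The case against.** The strongest reply is that the plan has safeguards and the size is assumed.

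- **Exclusion at COPD diagnosis.** It removes cancers already recorded by then. That narrows the problem, but both groups named above remain.
- **Adherence rule.** Patients whose early cancer led to death or stopping would tend not to reach more than 10 inhalers in a year, which would lower the year-1 share of cancers. The text does not say which 12 months are meant, and patients who continue treatment still count. The rule weakens the assumed 20% to 40% but does not replace a lag.
- **Text not visible.** Section 9.3 defers detailed definitions to a separate SAP. The checklist cites a section 9.7.3 for sensitivity analyses that is not in the visible text. A lagged analysis may exist there. A reader might infer that the sponsor chose a zero lag throughout, but the documents support only that the visible main analysis states none. A sensitivity analysis elsewhere would not change that main analysis.
- **Size.** A reader might infer that the hazard ratio is certainly distorted. The documents do not support this: the rates and imbalances were put in by assumption, and equal pre-existing cancer leaves a true null unchanged. Nor does the plan claim causation, since section 9.9.5 speaks only of correlation.
- **Lag length.** It is a judgement. This argues for reporting several lags, not for having none.

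**Conclusion.** The point stands for one secondary outcome. No primary endpoint is affected. As visibly written, cancers recorded between COPD diagnosis and the index date, or undiagnosed at the index date, can be counted as incident.

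Equal numbers in the two arms pull a true effect towards 1. Unequal numbers bias the HR either way, which is possible with smoking usually unavailable. Neither size nor direction can be derived from the documents. As illustration only, a true HR of 1.30 appears as 1.23 to 1.17 if 20% to 40% of events fall in year 1 and carry no effect. A two-fold imbalance in undiagnosed cancer (0.5% against 1%) moves a true null to 1.17 or 0.85 at the central assumed values. The change is worth making because it is cheap and targets a stated rule.

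**What to change.** In 9.3.2.2 and 9.7.2, for the lung cancer outcome only:

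1. Exclude patients with any C34 code on or before the index date.
2. Start risk time after a pre-specified lag, for example 12 months, and drop patients with a C34 code within it.
3. Report the no-lag result and other lags, for example 6 and 24 months, alongside.
4. Re-check covariate balance in the lagged cohort. Section 9.7.1.1 itself warns that balance is not automatically kept in sub-cohorts, and dropping one member breaks a matched pair, so state how broken pairs are handled.
5. If the SAP or the redacted text already holds a lagged analysis, align the main analysis with it.

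The cost is a wording change and a new start date for one outcome, on existing data. The downside is lost information: about one fifth of person-time, and possibly 20% to 40% of events under the assumed shares, which widens the confidence interval by about 12% to 29% on the log scale. Because the no-lag result is still reported, nothing now planned is lost.

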9.3.3 Covariates

Age, sex and history of COPD exacerbation, income status(quartile) or medical health insurance are all matching factors and will thus inherently be accounted for.

9.4 DATA SOURCES

Korea National Health Insurance claim data & mortality data from the Bureau of Statistics from Jan 2005 to Apr 2016 will be used for this study. It includes computerized medical records of more than half million patients practices in South Korea.

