9. RESEARCH METHODS

9.1 STUDY DESIGN

This is a non-interventional, single-country study based on existing data from medical records of patients in Korea National Health Insurance claim data & mortality data from the Bureau of Statistics from Jan 2005 to Apr 2016. This is a retrospective review study of nationwide cohort, which analyses the claims data of the entire Korean population.

In total, at least 10,000 eligible patients are planned to be enrolled to this study.

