9.7.1 Analysis Dataset : Patients selection

The matching between LAMA[Spriva® HandiHaler® Respimat® (Tiotropium Bromide Monohydrate)] and ICS/LABA are performed by sex, age category (5 year spans above 55 years), years since diagnosis of COPD, as available in the database, and propensity score.

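### The stated data window (January 2005 to April 2016) conflicts with an inhaler-naive exclusion that needs prescriptions from 2002; unless earlier claims are extracted, early entrants have little or no look-back

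*Combined protocol and SAP*

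**What the plan says.** Section 9.4 states that claims data and "mortality data from the Bureau of Statistics from Jan 2005 to Apr 2016 will be used for this study". Section 9.1 and the abstract give the same dates, and section 9.2 adds: "The maximal observation period will be from Jan 2005 to Apr 2016". Section 9.7.2 describes the whole of the available data as giving at most 11 years of follow-up.

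Entry opens on the first day of that window. Section 9.2 takes patients who "initiated LAMA or ICS/LABA more than twice a year from Jan 1, 2005 to Apr 30 2016".

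The new-user exclusion in the same section reaches further back. It removes patients with "Prescription history with any long acting bronchodilator for maintenance therapy", and its parenthesis and dates read "the patient should be inhaler naïve) from 2002 to 2005". The abstract uses the same years. A further exclusion, "Prescription history with Leukotriene receptor antagonist(LTRA) or ICS", has no dates.

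Section 9.7.1 matches directly on sex, age band and "years since diagnosis of COPD, as available in the database", together with the propensity score. Section 9.7.1.1 puts exacerbation history, Charlson index and asthma history into the score. Section 9.12 adds earlier and concurrent use of other drugs. No look-back length is stated for any of these. The variable list in Annex 3 gives no extraction years.

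**The concern.** An exclusion can only be applied to claims that are in the extract. If the extract begins when enrolment begins, a patient who has used ICS/LABA since 2003 and whose first visible claim falls in early 2005 looks like a new user. That patient would also appear to have no exacerbation history, a low Charlson index and a recent COPD diagnosis.

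Two things are at stake. First, section 9.12 relies on follow-up starting at the initiation of drug use. An ongoing user's first visible claim is not an initiation, and such patients have already come through early treatment. Second, the matching variables would rest on almost no history for a 2005 entrant and on about ten years for a 2015 entrant. Calendar year of entry is not a listed matching or propensity factor. The balance criterion (standardized difference below 0.1) would not reveal the problem, because unseen history counts as absent in both arms. If use before 2005 differed between the two drugs, the arms would be contaminated unequally, and the pneumonia, exacerbation and mortality comparisons could be distorted in a direction that the documents do not determine.

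**Working it through.** **Inputs.** Data window January 2005 to April 2016 (abstract, 9.1, 9.4; the same dates are the observation period in 9.2). Entry from 1 January 2005 (9.2). Exclusion window 2002 to 2005 (abstract, 9.2). Maximum follow-up of 11 years (9.7.2). Study size of at least 5,000 per arm, about 200,000 COPD patients a year, with LAMA and ICS/LABA use of 26% to 37% (9.5). The 12- and 36-month look-backs used below are assumptions: 36 months is the length of 2002-2004, and 12 months is a common shorter choice.

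**1. Reproduce the plan's follow-up figure.** January 2005 to April 2016 is 11 × 12 + 4 = 136 months, and 136/12 = 11.33 years. This agrees with the stated 11 years. A January 2002 start would give 136 + 36 = 172 months, or 14.33 years of data. Section 9.7.2 therefore fits data that begin in January 2005, with follow-up starting at about the first day of data and nothing before it.

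**2. Look-back inside the stated data** (entry month minus January 2005):
- entry January 2005: 0 months
- entry December 2005: about 11 months
- entry January 2015: 120 months, or 10 years

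**3. Coverage of the exclusion window.** Of the 36 months in 2002-2004, 0 lie inside the stated data. If 2005 is counted as part of the window, 12 of 48 months do (25%).

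**4. Share of the enrolment window without a full look-back.**
- 12-month look-back: 12/136 = 8.8%, about 9%
- 36-month look-back: 36/136 = 26.5%, about 26%

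These are shares of calendar months. They would be shares of patients only if entry were even over the period, which the documents do not say.

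**5. Follow-up left if the look-back must fit inside the stated data.**
- 12 months, entry from January 2006: (136 − 12)/12 = 10.33 years
- 36 months, entry from January 2008: (136 − 36)/12 = 8.33 years

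With extraction from January 2002, entry from January 2005 keeps both a 36-month look-back and 11.33 years.

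**6. Patient numbers.** 200,000 × 26% = 52,000 and 200,000 × 37% = 74,000 users a year. The 5,000 per arm is 9.6% and 6.8% of these. They are all users in a year, not inhaler-naive initiators, so they do not show how many eligible starters would remain after a later opening.

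**The case against.** The strongest reply is that the exclusion itself names 2002, which suggests that the authors expect to hold claims from then. January 2005 to April 2016 would then be the follow-up period, as the observation-period wording in 9.2 could be read. The sentence in 9.4 is also ambiguous: its dates may belong to the mortality data alone. On either reading, no bias need arise for 2005 entrants. This stands as a reason not to treat contamination as established. It does not remove the conflict. Section 9.4 is the data-source section, 9.7.2 ties the available data to 11 years, and no text says that earlier claims will be requested. If the dates belong only to mortality, the claims extract has no stated start.

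A second reply reads 2002 to 2005 as including 2005, so that an ongoing user with a 2005 claim is excluded. That would also exclude everyone who starts in 2005, against the inclusion criterion, and would cap follow-up at 10.33 years.

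A third is that the protocol defers detailed variable definitions to an SAP, which could set the covariate look-back; no separate SAP text is among the documents. Section 9.7.1 also qualifies years since diagnosis by availability. Both points are fair for the covariates, though the qualification covers only that one variable. The data window and the exclusion dates are in the protocol itself.

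A reader might also put a figure on the contamination. If ongoing users in January 2005 equalled one to two years of starts, they would be 1/12.33 = 8% to 2/13.33 = 15% of an arm's apparent initiators. The documents give no such stock, and the steady starts assumed here fit poorly with a cohort aged over 55 as of 2005. These percentages should not be used.

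**Conclusion.** The inconsistency is real and needs an edit whichever reading is intended. Followed as written, the plan cannot apply its inhaler-naive exclusion to 2002-2004. It leaves 2005 entrants with 0 to about 11 months of history, while later entrants have years.

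A reader might infer that ongoing users will in fact enter as new users and bias the comparisons. The documents support this only on the condition that the extract starts in January 2005. If 2002-2004 claims are obtained, this bias does not arise for 2005 entrants, and the error lies in the data-source text. Even under the condition, neither the number of patients affected nor the direction of bias can be computed. The 9% and 26% describe enrolment months under assumed look-backs of 12 and 36 months. The problem is concentrated in early entrants. It should be settled before the data request, because extraction and programming would follow the stated dates.

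**What to change.** In the abstract and in 9.1, 9.2 and 9.4, state an extraction period starting in January 2002, separate from the enrolment and follow-up period.

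Apply the inhaler-naive exclusion, and measure exacerbation history, Charlson index and asthma history, in one look-back of equal, stated length before each patient's first LAMA or ICS/LABA prescription. With data from January 2002, up to 36 months is available to every entrant.

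Treat years since COPD diagnosis differently. It is a direct matching factor, and a 12-month window would leave it almost no meaning. Take it from all available claims, in categories capped at the shortest history that every entrant has, for example three years or more.

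If 2002-2004 claims cannot be obtained, open enrolment only after one full look-back of visible data: January 2006 for 12 months or January 2008 for 36 months. The first gives one year of washout where the protocol's own dates imply about three. Reduce the stated maximum follow-up to 10.33 or 8.33 years accordingly.

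The cost of the main option is a longer extraction from the same database plus text edits. The cost of the fallback is one or three years of entrants. Before choosing it, count the eligible naive initiators against 5,000 per arm, because the yearly figures in 9.5 include prevalent users.
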